9.0 STATISTICAL ANALYSIS

9.1 Sample Size and Power Calculations

We will assess reduction in incidence of severe or invasive infections, with or without culture or PCR confirmation. Sample size is based on incidence of severe or invasive infections, using a baseline rate of 0.71 infections/child/year, derived from data of children from an earlier clinical trial conducted at MHSCC (the NOHARM study). Power calculations assume an alpha of 0.025 for a one-sided test or 0.05 for a two-sided test. With an incidence of 0.71 severe or invasive infections/year in the placebo group, a sample size of 250 children (with a 10% loss to follow-up) will have 80% power to detect a decrease of $\geq 40\%$ in severe or invasive infection incidence over the 12-month study period. This decrease is smaller than the 47-88% reduction in clinical infection incidence in adolescents and adults in previous studies⁶⁻⁸, so the study sample size should allow us to detect the expected effects of zinc on infection incidence.

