1.0 INTRODUCTION

1.1 Background and Rationale

Globally, 75% of all children with sickle cell anemia (SCA) are born in sub-Saharan Africa, approximately 240,000 children annually¹. Yet few research studies on interventions to prevent complications of SCA have been conducted in African children. Infection is a major cause of morbidity and mortality in African children with SCA. In our recently concluded hydroxyurea in SCA study, 37% of children with SCA had clinically severe infections (pneumonia, sepsis, bacteremia, or malaria) over the 12 months of study, and 2 of the 3 deaths in the study were attributed to sepsis. Prevention of infection could therefore significantly decrease morbidity and mortality in African children with SCA.

Zinc supplementation may provide a simple, safe and low-cost way to prevent infection in children with SCA. Zinc is important in development of T and B cell immune responses², and through its effects on these responses may help to prevent or reduce infection. In multiple studies in healthy children < 5 years of age, zinc supplementation reduced incidence of diarrhea and pneumonia with minimal side effects³. Zinc deficiency is common in adults and children with SCA, due to increased release of zinc during bone degradation in vaso-occlusive crises (VOC)⁴ and subsequent loss of zinc in the urine⁵. These losses are frequently not compensated because local diets that are consumed in many regions where SCA is most prevalent tend to be poor in zinc. In clinical trials in adults or adolescents with SCA, zinc supplementation decreased incidence of infection by 47-95% compared to placebo or to a prior period without zinc supplementation⁶⁻⁸. However, to date no zinc supplementation trials for prevention of infection have been conducted in children <5 years of age with SCA. Zinc may also have other beneficial effects in SCA, including decreased VOC, due to its effects on red cell hydration⁶⁻⁸, and improved growth⁹.

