1.3 Infection Causes Substantial Morbidity and Mortality in African Children with SCA

Infections in children with SCA are a major cause of hospitalization and mortality. The risk of infectious complications in SCA is most evident in low- and middle-income countries (LMICs), where access to care and treatment options are limited. Pneumococcal prophylaxis and pneumococcal vaccination have decreased invasive pneumococcal disease in SCA, but infection remains a common cause of significant illness in African children with SCA. For example, in the NOHARM study of hydroxyurea we recently conducted at the Mulago Hospital Sickle Cell Clinic (MHSCC), children with SCA had an average of 0.7 infections/child/year classified as “severe or invasive” infections (see Appendix I for infections that met this criterion). In addition, two of the three deaths that occurred in the first year of study were attributed to sepsis.

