4.6 Sample Size

A total 250 children, randomized to receive either zinc (n=125) or placebo (n=125)

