9.2 Proposed Analysis

We hypothesize that the incidence of infection in the zinc supplemented group will be $\geq 40\%$ lower than that of the placebo group. Incidence of clinical infection will be compared using Poisson or negative binomial regression analysis. Other factors that are potentially associated with the risk of infection will be included in the regression models as covariates. Analysis will be implemented using SAS PROC GENMOD or NLMIXED as appropriate. Similar analyses will be conducted for incidence of culture or PCR-confirmed bacterial infections, VOC, SAE and AE. Frequency of infection, culture or PCR-confirmed bacterial infection, VOC, AE and SAE will also be compared using χ^2 analyses.

We will conduct one interim analysis, for examination of the efficacy and futility of the trial. The interim analysis will be conducted at the time when we accumulate half of the expected outcome events. In the one-year follow-up period, we expect to see a total of 142 episodes of severe or invasive infections between the two trial arms. We plan to perform the interim analysis when we have 71 episodes of severe or invasive infections. We follow a symmetric two-sided group sequential design with 80% power and total 5% Type I error rate. Using the O'Brien-Fleming bounds, we determine the p values of spending function for the interim analysis to be 0.006. We will reject the null hypothesis when the p value of the interim analysis is less than 0.006.

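### The 80% power in 9.1 matches a Poisson calculation and allows at most very little for between-child variation, although 9.2 provides for negative binomial analysis

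*Combined protocol and SAP*

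**What the plan says.** Section 4.6 sets 250 children, 125 per arm. Section 9.1 builds the sample size on a placebo rate taken from the earlier hydroxyurea trial, "With an incidence of 0.71 severe or invasive infections/year in the placebo group", with a two-sided 5% test ("Power calculations assume an alpha of 0.025 for a one-sided test or 0.05 for a two-sided test"). It then states that "a sample size of 250 children (with a 10% loss to follow-up) will have 80% power to detect a decrease of" at least 40% over 12 months. It names no distribution, formula, variance or dispersion. It adds that 40% is below the 47-88% reductions seen in older patients, and concludes that the sample should be adequate for the effect expected.

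Section 9.2 plans "Poisson or negative binomial regression analysis" with risk factors for infection as covariates. That sentence speaks of clinical infection, but no other model is given for the primary outcome, so it reads as the primary analysis. The same section repeats 80% power for the group sequential design and expects 142 episodes. Section 6.3 adds hydroxyurea, prescribed at the clinicians' discretion, as a covariate.

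**The concern.** Poisson regression treats every child in an arm as having the same infection rate, apart from covariates. If children differ in risk, counts vary more than Poisson allows, the rate ratio is estimated less precisely, and power falls. A plan that names the negative binomial model and lists risk covariates accepts that such variation is possible. Its power statement should then carry some allowance for it, or say that it does not.

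Two things depend on this. A null result would be read against a 20% chance of missing a true 40% reduction, when that chance could be higher. And the argument in 9.1 that 40% sits safely below the earlier 47-88% loses its margin as the detectable reduction rises.

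**Working it through.** **Inputs.** From 9.1: placebo rate 0.71 per child-year; 40% reduction, so rate ratio 0.60 and zinc rate 0.71 × 0.60 = 0.426; two-sided 5%; 10% loss. From 4.6: 125 per arm, so 125 × 0.9 = 112.5 followed. Dispersion k, with variance = mean + k × mean², is not in the documents. It is an assumption, shown from 0 to 1.

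**Formula.** SE(log rate ratio) = √[(1/0.71 + 1/0.426 + 2k) / n]; power = Φ(|ln 0.60| / SE − 1.96). Here |ln 0.60| = 0.5108, 1/0.71 = 1.4085 and 1/0.426 = 2.3474.

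**The plan's own figure.** At k = 0 and n = 112.5, SE = √(3.7559/112.5) = 0.1827, and 0.5108/0.1827 − 1.96 = 0.836, so power is 79.8%. Other Poisson formulas give 80.7% (rate difference), 81.3% (square root) and 81.5% (pooled null variance). Comparing proportions with at least one infection gives 69%, so that is not the source.

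**Other routes to 80%.**
- Ignoring the loss (n = 125): 83.8% at k = 0, and 80.0% at k = 0.20. The 142 episodes in 9.2 equal 125 × (0.71 + 0.426), which also ignores loss.
- Lost children contributing half a year: the information per arm is 112.5μ/(1 + kμ) + 12.5(μ/2)/(1 + kμ/2). Power is 81.9% at k = 0, and 80.0% at k = 0.10.

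**Sensitivity to k** (112.5 per arm unless stated):

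| k | Placebo variance/mean (1 + 0.71k) | SE | Power, 40% reduction | Same, half-year dropouts | Reduction detectable with 80% power | Power, 47% reduction |
|---|---|---|---|---|---|---|
| 0 | 1.00 | 0.1827 | 79.8% | 82% | 40% | 92% |
| 0.25 | 1.18 | 0.1945 | 74.7% | 77% | 42% | 88% |
| 0.5 | 1.36 | 0.2056 | 70.0% | 73% | 44% | 85% |
| 1 | 1.71 | 0.2262 | 61.7% | 65% | 48% | 78% |

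The detectable reduction solves the power formula for the rate ratio at 80%. For a 47% reduction (rate ratio 0.53), power reaches 80% at k of about 0.86.

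**Checks.** Simulated negative binomial Wald tests (2,500 trials per setting, 113 and 112 children) gave 79.6%, 76.7%, 69.6% and 62.0% at k = 0, 0.25, 0.5 and 1, within about 2 points of the formula. The single interim look costs less than 1 point (79.5% at k = 0, 69.6% at k = 0.5).

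**The case against.** **The 80% is not an arithmetic error.** This stands: the figure reproduces. A reader might go further and infer that it can only be a pure Poisson figure. The documents do not support that, since 9.1 names no method and the two other routes above reach 80% with a small k.

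**No k is documented.** This stands too. A reader might infer that the true power is 60-75%; that is only what follows from k between roughly 0.25 and 1.

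**The evidence for clustering is thin.** A reader might compare "37% of children with SCA had clinically severe infections (pneumonia, sepsis, bacteremia, or malaria) over the 12 months of study" in 1.1 with "children with SCA had an average of 0.7 infections/child/year" in 1.3 and infer heavy clustering, because Poisson at 0.71 predicts 1 − e^(−0.71) = 51% with at least one infection. But the 37% covers a narrower list, and a Poisson rate of 0.46 for that list gives exactly 37% (−ln 0.63 = 0.46). It says nothing about k. Nor does a composite endpoint create overdispersion by itself, because a sum of independent Poisson counts is Poisson.

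**Some of the loss may be recovered.** The k that matters is what remains after covariate adjustment. The 0.71 comes from Kampala, which 6.3 describes as having much lower malaria transmission than the study site. With 112.5 per arm, a placebo rate of 0.82 would restore 80% at k = 0.25, and 0.97 would at k = 0.5. The study-site rate is unknown, however, 6.3 also adds bednets to existing prophylaxis, and 9.1 claims neither gain.

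**The expected effect is larger than 40%.** This limits the consequence, as the last column of the table shows, but the plan states its power for 40%.

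Analysing overdispersed counts with plain Poisson regression is no way out: simulated two-sided type I error was about 9% at k = 0.5 and 13% at k = 1.

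**Conclusion.** Wrong as written: 9.1 and 9.2 state 80% power for a 40% reduction without condition, and the design does not deliver it under the overdispersion that the planned analysis allows for beyond a very small amount (k above 0.20 on the most generous of the readings examined). Over k = 0.25 to 1 the shortfall is about 5 to 18 points with 112.5 followed children per arm, or about 3 to 15 points if lost children contribute half a year.

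This rests on the rate of 0.71 holding at the study site, on no gain from covariates, and on an assumed k. The claim that the trial can detect effects of the size seen before is more robust. It survives at 47% until k is about 0.86 and fails only narrowly at k = 1. The point is that the stated power is conditional and the condition is missing, not that the trial is shown to be too small.

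**What to change.** In 9.1:
- Name the power method, the variance assumption and how the 10% loss enters.
- Estimate k from the child-level counts of the earlier trial that supplied the 0.71. According to 3.0 the same investigators ran it, so the counts should be within reach.
- Replace the unconditional 80% with negative binomial power for a 40% reduction, and the reduction detectable with 80% power, at that k and over a range such as 0 to 1.

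Make the 80% in 9.2 agree. The cost is one calculation and some wording. Enrolment, visits and the analysis model are unchanged. The downside is that the stated power becomes less favourable.

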9.2 Proposed Analysis

We hypothesize that the incidence of infection in the zinc supplemented group will be $\geq 40\%$ lower than that of the placebo group. Incidence of clinical infection will be compared using Poisson or negative binomial regression analysis. Other factors that are potentially associated with the risk of infection will be included in the regression models as covariates. Analysis will be implemented using SAS PROC GENMOD or NLMIXED as appropriate. Similar analyses will be conducted for incidence of culture or PCR-confirmed bacterial infections, VOC, SAE and AE. Frequency of infection, culture or PCR-confirmed bacterial infection, VOC, AE and SAE will also be compared using χ^2 analyses.

We will conduct one interim analysis, for examination of the efficacy and futility of the trial. The interim analysis will be conducted at the time when we accumulate half of the expected outcome events. In the one-year follow-up period, we expect to see a total of 142 episodes of severe or invasive infections between the two trial arms. We plan to perform the interim analysis when we have 71 episodes of severe or invasive infections. We follow a symmetric two-sided group sequential design with 80% power and total 5% Type I error rate. Using the O'Brien-Fleming bounds, we determine the p values of spending function for the interim analysis to be 0.006. We will reject the null hypothesis when the p value of the interim analysis is less than 0.006.

10.0 HUMAN SUBJECTS

10.1 Protection of Human Subjects

This protocol, the informed consent document, patient recruitment brochures, and any subsequent modifications will be reviewed and approved by the local Institutional Review Board responsible for review and approval of the study (Makerere University School of Medicine Research Ethics Committee), as well as the Indiana University IRB. Compliance with GCP guidelines for the conduct and monitoring of this clinical trial will occur through observation of the ethical and regulatory requirements presented in ICH E6, Good Clinical Practice: Consolidated Guideline. The Investigators will comply with all clinical trial disclosure and registration regulations. Approval of the local Ethics Committee will be received prior to initiation of the study, along with IRB approval by Indiana University.

10.2 Informed Consent Process

Written informed consent will be obtained from the parent or guardian of subjects since they are below the legal age for consent or assent. A notation that written informed consent was obtained will be made on the subject's case report form. The original informed consent form will be retained at the study site; a copy will be put in the subject's records. A copy of the consent form will also be provided to the parent or guardian.

10.3 Confidentiality

All ZIPS laboratory specimens, evaluation forms, reports, and other records will be identified by a coded number to maintain subject confidentiality. All records will be kept in a locked file cabinet. Databases accessible to study personnel other than the PIs and data clerks and managers will include coded numbers only. Identifying information will not be released by the ZIPS data center without written permission of the subject/parent/guardian, except as necessary for monitoring. Clinical information can be shared by the site investigators and staff for patient care reasons, e.g., local consultations.

10.4 Data and Safety Monitoring Board (DSMB) and Stopping Rules

The DSMB will consist of 4 individuals, Drs. [name] (pediatrician, nutrition expert), [name] (pediatrician, malaria and sickle cell research expert), [name] (pediatrician, clinical sickle cell care and research expert) and [name] (biostatistician). The DSMB will meet every 6 months via Skype or other teleconference. The DSMB will review the data and provide guidance on study conduct and continuance. DSMB members will be independent and look at the trial from an ethical point of view of the participant safety, future patients and society in general. It is the responsibility of the DSMB to prevent patients being exposed to any excess risks by recommending to the study team and sponsors for trial suspension or termination early if SAEs appear to differ between study groups. The trial statistician will be invited to attend part of the DSMB meeting to present the most current data from the trial. This will be blinded, unless the DSMB specifically requests an unblinded analysis. If an unblinded analysis is requested by the DSMB, it will be provided to them and not to study personnel. Each DSMB member will be expected to serve for the duration of the trial. If a member is unable to continue participation, the reason will be documented and a replacement will be selected by the sponsor.

Stopping rules will be created for SAEs and for efficacy. Serious adverse events (SAEs) will be compiled and reviewed internally by the safety officer of the DSMB. Full SAE information will also be provided to the DSMB for review during the 6-monthly board meetings. Final stopping rules for SAEs will be developed by [name] (study biostatistician) in conjunction with the DSMB. Our proposed stopping rules for the DSMB are that the the study statistician, who will be unblinded to the treatment assignment, will calculate the SAE rates in the cumulated sample, as well as in the two treatment groups. Summary results will be reported back to the DSMB in a blinded fashion (e.g., treatment "A" versus treatment "B"). The statistician will calculate the 95% confidence interval for the control group's rate of SAEs and compare the intervention SAE rate against the confidence limits. If the SAE rate of the intervention group falls outside of the 95% confidence limits of the control group rate, which means there is a strong chance that the two treatment groups have different SAE rates, the study statistician will bring the issue of early stopping for safety reasons to the DSMB. The DSMB will then make an informed decision on whether to recommend that the trial be stopped early on the basis of SAEs. This safety stopping rule will not affect the power of the efficacy analysis.

Similarly, stopping rules for efficacy will be based on whether the interim analysis provides strong evidence in support of the intervention efficacy. As described in the plan for interim analysis, if the p value for the comparison of severe infection rates was less than 0.006, the study statistician will bring the issue of early stopping for efficacy reasons to the DSMB. The DSMB will then make an informed decision on whether to recommend that the trial be stopped early based on evidence of efficacy.

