4.8 Randomization and Blinding

Block randomization will be used. The study pharmacist will have identical appearing zinc or placebo tablets and will provide the appropriate medication to the child. Children will be randomized (in blocks of 8) into treatment groups by order of entry in the study, based on a pre-determined blinded randomization list created and managed by an Indiana University study data manager. Treatment group will be provided to the study pharmacist, who will know only that the child is randomized to group A or B, but will not know which group is zinc or placebo. The designation of A or B on packets will be removed by the pharmacist prior to providing study drug to the child, so the medication will appear identical to study staff and parents/children. The child's study identification number will be recorded and treatment group may only be determined by comparing the child's study id to the blinded list, which only the IU data manager will have access to until the study is completed or stopping rules are reached.

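### Section 4.8 reserves the allocation list to the data manager while 10.4 unblinds the study statistician during the trial, and nothing fixes the primary model before results by arm exist

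*Combined protocol and SAP*

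**What the plan says.** **Access to allocation (4.8).** A child's arm can be found only by matching the study number to a list "which only the IU data manager will have access to until the study is completed or stopping rules are reached". The pharmacist "will know only that the child is randomized to group A or B, but will not know which group is zinc or placebo". No statistician is mentioned.

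**Use of allocation (10.4).** For the proposed safety rule, "the study statistician, who will be unblinded to the treatment assignment, will calculate the SAE rates in the cumulated sample" and in each group. The statistician then forms a 95% interval for the control rate, and is to "compare the intervention SAE rate against the confidence limits". The same person alerts the DSMB if the interim comparison of severe infections gives p below 0.006.

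**What the DSMB sees (10.4).** "Summary results will be reported back to the DSMB in a blinded fashion", as A versus B. On the trial statistician's presentation: "This will be blinded, unless the DSMB specifically requests an unblinded analysis". And: "If an unblinded analysis is requested by the DSMB, it will be provided to them and not to study personnel".

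**The analysis (9.2).** "Incidence of clinical infection will be compared using Poisson or negative binomial regression analysis". The covariates are other factors possibly related to infection risk, with no list. The only one named elsewhere is hydroxyurea (6.3), which clinic staff may prescribe during the study. There is no rule for choosing the model, no date for fixing it, and no mention of a separate blinded analyst.

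**The concern.** Read literally, 4.8 and 10.4 cannot both be followed. One makes the data manager the only person able to identify arms while the trial runs; the other has the statistician working with identified arms over the same period.

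This matters beyond tidiness because of 9.2. A statistician who sees results by arm is ordinarily harmless if the primary analysis is already fixed, or if someone else makes the remaining choices. Here neither safeguard is written down. The model sentence in 9.2 also names clinical infection, which is a secondary outcome, so the model for severe or invasive infections is not strictly stated at all. If the model and covariates are settled after results by arm have been seen, or could have been, the nominal 5% of the primary test is no longer assured, and the sponsor cannot show from the documents that it was.

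**Working it through.** **1. The access rules side by side.** The exception in 4.8 for a stopping rule being reached does not cover the statistician. The safety rule compares the intervention rate with the control interval, so the arms must be known in order to find out whether the rule has been reached. The statements within 10.4 do fit together: an unblinded statistician prepares output, shows it coded by default, and gives an identified version to the DSMB alone on request. The conflict is therefore between 4.8 and 10.4.

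**2. The plan's own figures (9.1, 9.2).** Placebo rate 0.71 per child-year, 40% reduction, so zinc rate 0.6 × 0.71 = 0.426.
- Events: 125 × (0.71 + 0.426) = 142.0, as stated.
- Power with 125 × 0.9 = 112.5 per arm: SE = √[(1/0.71 + 1/0.426)/112.5] = 0.183; |ln 0.6|/SE = 0.511/0.183 = 2.80; Φ(2.80 − 1.96) = 79.8%, against the stated 80%.

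Both reproduce, under Poisson variance with no overdispersion. Neither is in dispute.

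**3. One fixed Poisson model under the null.** Mean rate μ = (0.71 + 0.426)/2 = 0.568. With overdispersion k (assumed), the variance is inflated by φ = 1 + kμ, and a nominal 5% Poisson test rejects with probability 2[1 − Φ(1.96/√φ)].
- k = 0.5: φ = 1.284, 1.96/1.133 = 1.730, giving 8.4%.
- k = 1.0: φ = 1.568, 1.96/1.252 = 1.565, giving 11.8%.
- If two prognostic covariates (assumed log-rate 0.3 per SD, log-scale variance 2 × 0.09 = 0.18) are left out, total dispersion is (1 + k)e^0.18 − 1 = 0.796 or 1.394. Then φ = 1.452 or 1.792, giving 10.4% or 14.3%.

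**4. Adding the freedom to choose.** Null simulations with 125 per arm, rate about 0.57, 10% partial follow-up, and Poisson or negative binomial with or without two baseline covariates. Rejection at nominal 5%:

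| Setting | Model | k = 0 | k = 0.5 | k = 1.0 |
|---|---|---|---|---|
| Covariates unrelated to risk (1,500 trials) | One fixed Poisson | 4.1% | 9.0% | 13.8% |
| | Best of four | 4.8% | 9.7% | 14.5% |
| | One fixed negative binomial | 3.9% | 6.1% | 7.3% |
| | Best of two negative binomial | 4.3% | 6.4% | 8.0% |
| Prognostic covariates, 0.3 per SD | One fixed Poisson | 6.1% | 10.9% | 14.6% |
| | Best of four | 6.7% | 12.2% | 17.1% |

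In a further run with two prognostic covariates (3,000 trials), one fixed adjusted negative binomial model gave 4.6 to 5.6%, and the better of two negative binomial models 6.0 to 7.6%.

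The best of four cannot reject less often than a Poisson model in the menu, so 8.4% is a floor at k = 0.5. The highest four-model result is 17.1%. Hence roughly 8 to 17%.

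**5. What choosing adds, at k = 0.5 and 1.0.**
- Over one fixed Poisson model: 0.7 and 0.7 points with unrelated covariates (9.7 − 9.0; 14.5 − 13.8); 1.3 and 2.5 points with prognostic ones (12.2 − 10.9; 17.1 − 14.6).
- Among two negative binomial models: 0.3 and 0.7 points in the table, and up to about 2 points in the 3,000-trial run (7.6 − 5.6).

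**6. Sensitivity to the covariate menu.** With four candidate covariates (16 sets, 112 per arm, 500 trials), the best negative binomial set gave 8.4% and 11.8% at k = 0.5 and 1.0, against 6.6% and 7.8% for one fixed fully adjusted model: 1.8 and 4.0 points more, with a simulation error of 1 to 2 points. A longer unlisted menu leaves more room.

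**The case against.** **Unblinded reporting statisticians are common.** True, and access alone is not the defect. What stands is that 4.8 excludes it and that no separation or fixed model accompanies it.

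**The final analyst is not named.** A reader might infer that the unblinded statistician will run the final analysis and pick the model. The documents do not say so; 9.2 assigns the analysis to nobody in particular. Nor do they say that this person computes the interim comparison, only that he or she takes the result to the DSMB. The supportable statement is that nothing prevents it.

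**The DSMB is not kept in the dark.** A reader might infer that the usual protection is inverted, with the board masked and the analyst not. Coded output is only the default. The board includes a biostatistician and may ask for identified results. The safety rules are also described as proposals to be finalised with the board.

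**The inflation is not caused by unblinding.** This largely stands. A fully blinded, prespecified Poisson analysis would show most of the same excess, and at zero dispersion the best of four gives only 4.8 to 6.7%. Conversely, a statistician blinded until database lock could still choose a model afterwards if none were fixed. The type I error argument therefore rests mainly on 9.2; the access conflict is what makes timing matter.

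**Moving the work to the data manager.** That would place comparative results with staff who handle live data, and nothing shows that this person could run a group-sequential analysis. It should not be required.

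**Conclusion.** The conflict between 4.8 and 10.4 is in the text and needs no assumption. The absence of a fixed model, a covariate list and a separation of roles is equally plain. Together they leave open that the primary model is settled after results by arm are seen; this is a risk, not a stated plan.

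The sizes are conditional on assumed overdispersion of 0.5 to 1.0 and on assumed covariate effects, and they describe deliberate selection of the smallest p-value, so they are not predictions. On those terms, false rejection is roughly 8 to 17%. About 8 to 14% arises from a single Poisson model, and about 0 to 2 points from choosing between two negative binomial models, more if the covariate menu is long. A reader might take the whole excess as the cost of unblinding; steps 3 and 5 of the working show otherwise. Nor does the conflict show that masking of families, clinic staff or the pharmacist fails. The point should be corrected, but it does not invalidate the design.

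**What to change.** 1. In 4.8, name every role with arm-level access during the trial and the purpose of that access. Make 10.4 say the same, including whether the unblinded statistician counts as study personnel.
2. State that whoever has that access takes no part in model or covariate decisions for the final analysis. Who runs the by-arm programs can be left to the sponsor.
3. Before the first output by arm, whether for safety or for the interim analysis, sign an SAP that fixes the primary analysis of severe or invasive infections: negative binomial regression with a log person-time offset, a listed set of baseline covariates, and a rule for counting events.

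The cost is wording in two sections and an earlier SAP sign-off. The model choice also makes one thing visible. With k added to each term of the power formula, SE² = (1/0.71 + 1/0.426 + 2k)/112.5, and power is 70.0% at k = 0.5 and 61.7% at k = 1.0. That loss comes from the assumed overdispersion, not from the fix; under Poisson it would be hidden rather than avoided.
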